AIM 1: To evaluate hyperarousal and hopelessness as interacting mechanisms by which perimenstrual E2+P4 withdrawal (vs. experimental stabilization) increases proximal suicide risk. We predict that **(1a)** individuals will demonstrate greater proximal suicide risk during perimenstrual E2+P4 withdrawal (placebo) than during perimenstrual E2+P4 stabilization, an effect mediated by **(1b)** indices of hyperarousal, **(1c)** indices of hopelessness, and **(1d)** their interaction (i.e., with hopelessness predicting suicide risk only during hyperarousal).

AIM 2: To evaluate neuroactive steroid withdrawal as a mechanism by which perimenstrual E2+P4 withdrawal (vs. stabilization) increases proximal suicide risk. We expect that E2+P4 withdrawal (vs. stabilization) will induce neuroactive steroid withdrawal to some degree in all participants. However, we predict that the effect of hormone withdrawal (vs. stabilization) on proximal suicide risk at each lab will be mediated by **(2a)** degree of reduction in serum neuroactive steroid levels and **(2b)** degree of reduction in mRNA expression for neurosteroidogenic enzymes. We will also evaluate

within-person links between neuroactive steroids and all behavioral constructs; if appropriate, a multilevel mediation model will test the full model in Fig. 1.

AIM 3: To characterize GABA_{AR} gene expression plasticity across the cycle in individuals with and without perimenstrual changes in affective and suicide risk. In the HC group, we hypothesize that gene expression for $\alpha 4$ and δ subunits (GABRA4 and GABRD genes, respectively) are upregulated and $\gamma 2$ (GABRG gene) is downregulated in the midluteal (high ALLO) and perimenstrual (ALLO decline) phases compared to the midfollicular phase (low ALLO). We also hypothesize that clinical group moderates the effect of cycle phase on GABA_{AR} composition, such that the group with perimenstrual increases in affective symptoms and suicide risk shows higher slope of midluteal-to-perimenstrual change in $\alpha 4$ and δ subunits, and lower $\gamma 2$ subunit replacement of δ subunit expression than the HC group.

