Testing Interactive Effects of Hopelessness and Arousal on Suicide Outcomes: Interactions among hopelessness and arousal will be examined as predictors of suicide outcomes and as mediators of the experimental effect. In order to test this, we examine day-to-day interactive effects of daily person-centered hopelessness (noted above) and daily person-centered arousal indices (noted above) predicting same-daily suicide outcomes (noted above). We predict that higher-than-usual hopelessness on a given day will predict greater same-day risk on suicide outcomes, but only when arousal is *also* higher than usual for that individual.

4. Evaluating Mediation Where Appropriate. Finally, each aim indicates that **mediation** will be explored as appropriate. Only when analyses indicate significant effects of the experiment on both the suicide outcome and any mediator, as well as significant associations between the person-centered variable (or interaction variable) and the suicide outcome, we will utilize methods provided by **Bauer, Preacher, and Gil (2006)** to construct a confidence interval for the level 1 indirect effect of experimental condition (condition X phase) on the suicide outcome via the mediator.

Testing for normative cyclical change in the HC group. Aim 3 seeks to characterize how gene expression for GABA_{AR} subunits varies across pre-specified menstrual cycle phase in response to hormonal change. In N=40 HC participants, we will run multilevel growth models to predict subunit gene expression (one model per gene) from specific cycle phase. We will test all pairwise comparisons between midluteal, perimenstrual, and midfollicular phases, controlling for ALLO level, to capture high P4 and ALLO states (midluteal), P4 and ALLO withdrawal (perimenstrual), and low P4 and ALLO (midfollicular).

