Statistical Analysis Plan

Project Title: Cyclical Neuroactive Steroid Changes, Arousal, and Proximal Suicide Risk: An Experimental Approach

Principal Investigator: [name]

Approved as of September 24, 2019

Statistical Analysis Plan

There are twelve total outcomes, which are specified and numbered (#) below. In order to better set up the power analysis details that follow, I have noted the anticipated intra-class correlations for each outcome (in red) and note from which preliminary data these estimates arise.

OUTCOME SPECIFICATION

- Suicide Outcome Variables. In our primary analyses, proximal suicide risk will be operationalized as (1) daily severity of suicidal ideation using the total score on the Adult Suicidal Ideation Questionnaire in the daily survey (ICC=.64 in K99 trial), (2) daily suicidal planning thoughts (dichotomous) on the daily C-SSRS phone risk screen (~10% of days were positive for planning in the K99 trial; ICC=.45 in K99 trial) and (3) daily suicide attempt (dichotomous; aborted, interrupted, or full) on the daily C-SSRS phone risk screen (~1.2% of days were positive for suicide attempt in the K99 trial; ICC=.12 in K99 trial).

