- Power in multi-level models has a unique consideration beyond sample size and alpha; it is dependent also on the intraclass correlation (ICC) and its implications for the independence of level-1 observations (i.e., the design effect). High ICCs indicate little variation of the outcome within a given person (i.e., stability of repeated observations within a given person), and suggest that the study's power depends more on the number of higher-level units. Low ICCs indicate high within-person variation within a given person and suggest that the study's power depends more on the number of lower-level units. As the ICC ranges from 0 to 1, the effective n will range from the number of lower-level units to the number of higher-level units. In general, the lower the ICC, the higher the power.
- Snijders and Bosker (1999; *Multilevel Analysis: An Introduction to Basic and Advanced Multilevel Modeling*) provide equations to determine the "Design Effect", which we have used to calculate the "effective lower-level N" based on our expected ICCs for each outcome and our expected number of raw observations with 85 completer participants (including 15% missing at daily level and an average of .25 missing visits per person). Once the design effect and effective N is calculated for a given outcome, one can calculate power to detect a given effect size (in our case, f² = .10) for a given number of these *effective* lower-level units (observations or visits)— see Table below for estimates for the current design. We considered a single fixed regression coefficient in a model with 3 predictors, one-tailed test, alpha=.004.
 

Variable	Measureme nt interval	ICC	Upper-Level Sample Size	Effective Lower- Level N based on ICC and Design Effect Equation	Power Achieved to detect f ² = .10
Suicidal Ideation	Daily	.64	85	130	.81
Suicidal Planning	Daily	.45	85	180	.93
Suicide Attempt	Daily	.12	85	542	.99
Beck Hopelessness Scale	Daily	.32	85	244	.98
Brief Agitation Measure	Daily	.26	85	292	.99
Accelerometer activity	Daily	.54	85	152	.88
Typing Speed Instability	Daily	.38	85	209	.96
HRV withdrawal in the lab	Labs	.50	85	163	.90
PEP shortening in the lab	Labs	.50	85	134	.83
Allopregnanolone in serum	Labs	.29	85	177	.93
PBMC gene expression for 3a- HSD	Labs	.50	85	134	.83
PBMC gene expression for 5a- reductase	Labs	.50	85	134	.83

1 R01 MH120843-01 (PI: [name])

Additional Requested Supplemental Table (2019-08-16)

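### Aim 1d treats the hopelessness-by-arousal product as a mediator, but the hormone effect on that product is second-order, depends on an unstated centring choice and has no power figure

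*Protocol*

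**What the plan says.** Protocol section 3.0 lists the interaction of hopelessness and hyperarousal as mediator 1d and explains it as "with hopelessness predicting suicide risk only during hyperarousal". Protocol section 10.0 and SAP Analytic Steps item 3 then say: "Interactions among hopelessness and arousal will be examined as predictors of suicide outcomes and as mediators of the experimental effect". The only test they describe uses "daily person-centered hopelessness (noted above) and daily person-centered arousal indices (noted above) predicting same-daily suicide outcomes". That tests the interaction as a predictor of the outcome. No model is given for the hormone effect on the interaction.

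Item 4 in both documents sets the precondition for a mediation analysis: "Only when analyses indicate significant effects of the experiment on both the suicide outcome and any mediator", together with "significant associations between the person-centered variable (or interaction variable) and the suicide outcome". If it is met, a confidence interval is built for the indirect effect through the mediator.

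The SAP opens with "There are twelve total outcomes, which are specified and numbered (#) below". These are three suicide outcomes and nine single mediators; the product is not one of them. The power basis is "We considered a single fixed regression coefficient in a model with 3 predictors, one-tailed test, alpha=.004".

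**The concern.** The hypothesis in Aim 1d concerns a slope: hopelessness should matter more when arousal is high. That is conditional (moderated) mediation. It needs a hormone effect on hopelessness and a hopelessness slope that changes with arousal. It does not need the hormone to shift the mean of the product.

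The product is a poor stand-in. A product of two centred scores is positive when both are high and also when both are low, so part of any rise cancels. How much cancels depends on where zero is placed. Two analysts following the same text could reach different answers from the same data. The claim that the two constructs interact to cause risk is part of the central hypothesis, so the estimand should be fixed before unblinding.

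**Working it through.** **Reproducing the plan's figures.** Effective N = 85 × 24 / (1 + 23 × ICC). For hopelessness (ICC .32) this is 2040 / 8.36 = 244.0; for suicidal ideation (.64) it is 2040 / 15.72 = 129.8. With f² = .10, three predictors and one-sided alpha .004, power is .988 and .816. The SAP table gives 244 and .98, and 130 and .81. These rows reproduce; the table has no row for the product.

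**Hormone effect on the product.** Let placebo perimenstrual days rise by dH and dA, with the other three condition-by-phase cells flat. The person mean absorbs a share c of the rise.

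| Cell | Centred means | Mean product (plus a common covariance) |
|---|---|---|
| Placebo perimenstrual | (1 − c)dH, (1 − c)dA | (1 − c)² dH dA |
| Other three | −c dH, −c dA | c² dH dA |

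The condition-by-phase effect has size [(1 − c)² − c²] dH dA = (1 − 2c) dH dA.

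- Midluteal level, c = 0: dH dA.
- 28-day person mean, c = 7/28 = .25: .50 dH dA.
- 52-day mean, assuming 7 or 10 raised placebo days plus 5 withdrawal days at .59/.75 of the rise: c = .21 to .27, giving .58 to .46 dH dA.
- Within condition, c = .5: zero.

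On the 28-day mean with equal effects d, the result is .5d²: .125 at d = .5, .27 at .73, .38 at .87 and .50 at 1.0.

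**In the plan's effect-size units.** With one of four equal cells raised by d, f² = d²/16, so f² = .10 means d = √1.6 = 1.26. The product contrast is then .5 × 1.6 = .80. With within-day correlation r, the product's variance averages 1 + r² + .60(1 + r), which is 1.87 at r = .3 and 2.32 at r = .6. Its f² is (.80/4)² / variance = .021 to .017, about a fifth of .10. The SAP's method at effective N 244 then gives power of .27 to .35. That method is pessimistic for a within-person contrast, so the direct simulation below is the better guide.

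**Simulated power for the effect on the product.** 85 completers, 7 days in each of 4 cells, 15% missing, 28-day centring, one-sided .004. Assumed, not from the documents: normal scores, within-day correlation about .4, lag-1 autocorrelation .3, and effect heterogeneity with SD half the mean.

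| Effect on hopelessness / arousal (SD) | Product | Hopelessness alone |
|---|---|---|
| .5 / .5 | .08 | .94 |
| .6 / .6 | .20 | about 1.00 |
| .73 / .73 | .46 | about 1.00 |
| .73 / .87 | .63 | about 1.00 |
| 1 / 1 | .96 | about 1.00 |
| 1.26 / 1.26 | 1.00 | about 1.00 |

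If arousal moves only .25 SD while hopelessness moves .73, product power is .01 to .06. At .73 / .73, midluteal centring gives .87 to .93 and within-condition centring about .01.

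**Two readings of the precondition.** Assumed outcome slopes are .3, .3 and .2 (hopelessness, arousal, product), with within-day correlation .3 to .6. Entries are the proportion of trials that pass.

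| Effects | Product must respond | Either single mediator suffices |
|---|---|---|
| .5 / .5 | .04 | .41–.49 |
| .73 / .50 | .14–.16 | .66–.72 |
| .73 / .87 | .57–.62 | .94–.96 |
| 1 / 1 | .93–.96 | 1.00 |

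**No precondition at all.** A 95% interval for the indirect effect through the product (correlation .4, no autocorrelation, product slope .2) excluded zero in 25% of trials at d = .5, 43% at .6, 71% at .73 and 94% at .87 with 28-day centring. With within-condition centring the figure was 2 to 4%. Joint significance of the hormone effect on hopelessness and the interaction slope was at least .99 throughout.

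**The case against.** A reader might infer that the plan requires a significant hormone effect on the product before mediation is tested. The documents do not say so. The precondition speaks of any mediator and names the interaction variable only for its association with the outcome. One fair reading is a hormone effect on hopelessness or arousal alone plus a significant interaction slope. This stands, but it does not settle the matter: the indirect effect is taken through the mediator, which for 1d is the interaction, so the effect on the product returns at that step.

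A reader might also infer that true mediation will usually fail. That is not supported either. The pilot coefficients are −.73 for hopelessness and −.87 for agitation, in unstated units. If they are person-SD units, product power is about .63, and near 1 SD the problem largely disappears.

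Within-condition centring is an extreme. Person-centring with days nested in participants points more naturally to a whole-person mean, for which the multiplier is .46 to .58. The zero case shows what the wording leaves open, not what is likely.

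Finally, the central hypothesis has withdrawal raising both constructs. An index that uses only the effect on hopelessness could be significant when arousal does not change. This is a fair criticism of plain moderated mediation, and the fix has to meet it.

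**Conclusion.** The concern holds in limited form and should be fixed. The indirect effect the plan would compute for 1d does not represent the stated hypothesis, varies with an unstated centring choice, and has neither a specified model for the hormone effect nor a power figure. On the 28-day mean, power for the hormone effect on the product is about .08, .20 and .46 at 0.5, 0.6 and 0.73 SD, against at least .94 for hopelessness alone. The risk is greatest where an arousal index responds weakly. The accelerometer and typing measures have no stated pilot hormone effect, so this cannot be excluded for them.

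The algebra assumes only that one cell moves and the others do not. The power figures also rest on the assumed correlation, autocorrelation, heterogeneity, slopes and normal scores; skewed or floored daily items would change them. Hypotheses 1a to 1c and Aim 2 are not affected.

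**What to change.** In Protocol section 10.0 and SAP Analytic Steps items 3 and 4:

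- State which days define the person mean.
- Replace the interaction as mediator with conditional mediation. Fit one model per suicide outcome with person-centred hopelessness, arousal, their product, condition, phase and condition by phase.
- Report the hopelessness indirect effect at low and high within-person arousal (for example −1 and +1 within-person SD), with a participant-level bootstrap interval for the index: hormone effect on hopelessness × interaction slope.
- Report the hormone effect on arousal alongside, and claim 1d only if withdrawal also raises arousal.
- State that a significant hormone effect on the product is not required.

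The cost is wording and some programming, with no new data. It should be done before unblinded analysis.

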In sum, although changes in neuroactive steroids (both serum levels and biosynthetic enzyme mRNA expression) have been strongly implicated behavioral phenotypes associated with suicide, no studies have examined the roles of state changes in neuroactive steroids on proximal suicide risk. The proposed study would examine the roles of trait-like differences and day-to-day changes in neuroactive steroids in proximal suicide risk, during a high-risk period in which neuroactive steroids are rapidly changing.

Premise for Aim 3

GABA-A Receptor Subunit Composition

Exploratory substudy of healthy controls (HC): The menstrual cycle leads to predictable, cyclical changes in GABAergic neuroactive steroids (e.g., ALLO). The GABA_{AR} has 19 known genes coding for subunits α 1-6, β 1-4, γ 1-3, δ , ε , θ , π and ρ 1-2⁶⁹, with the majority of receptors comprised of two α , two β , and one γ or δ subunit⁷⁰ (e.g., $\alpha\beta\gamma$ or $\alpha\beta\delta$), although subunit expression is highly plastic. Preclinical work shows that the potency of ALLO's positive allosteric modulatory binding to the GABA_{AR} depends on the subunit composition; for example, γ 2-containing receptors are less sensitive to ALLO than α 4-containing receptors, and δ subunits augment steroid potency⁷¹. Further, preclinical models show that P4 and ALLO levels alter gene expression (via mRNA) and/or protein levels (via Western blot) for the α 4 subunit⁷²⁻⁷⁴, δ subunit⁷⁵⁻⁷⁷, and γ 2⁷⁸⁻⁸¹ subunit, such that plasticity of the receptor is a function of reproductive cycles. However, no human studies have described how subunits change *normatively* across the cycle.

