3.0 Objectives/Aims

Our aim is to test the **central hypothesis** is that perimenstrual E2+P4 withdrawal induces rapid withdrawal from calming GABAergic neuroactive steroids, which in turn increases hyperarousal and hopelessness, which then interact to cause proximal suicide risk (Figure 1). P4 is metabolized to GABAergic neuroactive steroids, and E2 promotes expression of enzymes that convert P4 to neuroactive steroids⁹³. Perimenstrual E2+P4 withdrawal may increase suicide risk by causing rapid withdrawal from the antidepressant⁹ and sedative^{11,10} effects of neuroactive steroids⁹⁴, as well as withdrawal from the antidepressant effects of E2⁹⁵. Our preliminary experimental work strongly suggests that perimenstrual E2+P4 withdrawal (and neuroactive steroid withdrawal) heightens proximal suicide risk via hopelessness⁶⁵ and hyperarousal^{12,66}.

Figure 1. Peri-menstrual Hormone Withdrawal and Proximal Suicide Risk

Design: Using the PI’s hormone withdrawal paradigm (K99MH109667¹²), a new sample of 90 completers female outpatients with past-month SI will complete two counterbalanced conditions: (1) natural perimenstrual E2+P4 withdrawal (placebo), and (2) perimenstrual E2+P4 stabilization. Five labs per condition will capture changes in neuroactive steroids, mRNA expression for neurosteroidogenic enzymes, physiological arousal, behavioral indices of arousal, and interview/self-report indices of proximal suicide risk, hopelessness, and hyperarousal. Our app (BiAffect) will passively track indices of arousal including psychomotor agitation (accelerometer) and reactivity (typing speed variability). Additionally, Metricwire will passively track movement using smartphone sensors. 40 healthy controls (HC) will complete five labs across one observational cycle to characterize 1) normative cycle-related variation in neuroactive steroids and mRNA expression, and 2) group-related differences (i.e., past-month SI vs HC) in trajectories of GABAAR subunit change across the cycle.

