Using Metricwire App		X	X	X		X			

Table 1b. substudy activities and timeline.

The proposed substudy characterizes 1) normative cycle-related variation in neuroactive steroids and mRNA expression, and 2) group-related differences (i.e., past-month SI vs HC) in trajectories of GABAAR subunit change across the cycle. 60 healthy controls (HC) with no SI will be recruited to gain a completer number of 40 for a two-month long observational substudy, in which five lab visits across one menstrual cycle (timed identically to mirror the observations across one medication phase of the experimental trial) will capture baseline molecular/genetic changes for between-group comparisons. The basic timeline for participation can be seen in table 1b.

The **double-blind crossover experimental design** is identical to that used during the PI's recently-completed trial (K99MH109667; Fig. 6). The TOP (red) panel shows natural perimenstrual hormone withdrawal in the placebo condition; the BOTTOM (black) panel shows prevention of hormone withdrawal in the active E2+P4 stabilization condition. THIS IS NOT A CLINICAL EFFICACY TRIAL, but a RCT design will probe the effect of hormone withdrawal (vs. stabilization) on proximal suicide risk and mediators. Participants will be randomized to condition order A (see Table 1 above; Active E2+P4, washout cycle, then Placebo) or condition order B (Placebo, washout cycle, then Active E2+P4). Investigational Drug Services will manage the double-blind. In each two-week condition, participants will wear a weekly patch (E2 or placebo) and take a daily pill (P4 or placebo). Because this manipulation simply delays natural E2+P4 changes⁹⁶, and given our previous finding of benefit¹², this manipulation is *not expected to pose greater risk than a normal menstrual cycle*.

Timing and Duration. Participants will receive the first seven-day transdermal E2 patch (or placebo patch) and begin daily oral P4 (or oral placebo) at a lab visit scheduled seven days after a positive urine ovulation test (+7 in Fig 6). This coincides with a time in the natural cycle when E2+P4 are already elevated. The weekly patch will be changed at the lab visit on day +14. The goal of this E2+P4 manipulation is to extend and maintain the mid-luteal phase hormone profile beyond the point in the cycle (i.e., around day +10) that would normally be associated with natural hormone withdrawal. Therefore, the active condition effectively prevents perimenstrual E2 and P4 withdrawal.

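### Aim 3 healthy-control phase contrasts are stated only with adjustment for ALLO level; if that means the visit-level value, they do not estimate the total phase differences hypothesised in Protocol section 3.0

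*Protocol*

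**What the plan says.** **Hypothesis.** Protocol section 3.0, Aim 3, predicts for HC that γ2 expression is "downregulated in the midluteal (high ALLO) and perimenstrual (ALLO decline) phases compared to the midfollicular phase (low ALLO", with α4 and δ moving the opposite way in the same phases. Nothing is held fixed, and the phases are labelled by their ALLO state.

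**Purpose.** Section 10.0 (normative cyclical change in the HC group) aims to show how subunit expression "varies across pre-specified menstrual cycle phase in response to hormonal change". Section 6.0 says: "The proposed substudy characterizes 1) normative cycle-related variation in neuroactive steroids and mRNA expression". The reason given in section 2.0, Premise for Aim 3, is: "However, no human studies have described how subunits change" over a normal cycle.

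**Planned test.** In 40 HC, with one model per gene: "We will test all pairwise comparisons between midluteal, perimenstrual, and midfollicular phases, controlling for ALLO level, to capture high P4 and ALLO states (midluteal". The sentence goes on to label the perimenstrual phase as P4 and ALLO withdrawal and the midfollicular phase as low P4 and ALLO. No HC contrast without ALLO is stated.

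**Premise.** Section 2.0 describes ALLO as low in the follicular phase, highest midluteally and falling perimenstrually. It also says that in preclinical models "P4 and ALLO levels alter gene expression (via mRNA) and/or protein levels (via Western blot" for the α4, δ and γ2 subunits.

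**What is not said.** Neither document states whether the ALLO term is the visit value, the person's mean or a baseline value. Section 10.0 defines a person-mean and deviation split for subunit expression only. ALLO is measured at every HC visit, so a visit-level covariate is available. The SAP lists twelve outcomes, all for Aims 1 and 2, and does not cover Aim 3.

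**The concern.** The hypothesis concerns the whole difference in expression between phases, including the part that hormones produce. On the protocol's account, phase changes ALLO and ALLO helps to change expression. Adjusting for ALLO at the same visit asks a different question: how far the phases differ at equal concurrent ALLO. The planned sentence pulls in two directions, because it holds ALLO constant in order to capture states that it defines by their ALLO.

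At stake is the interpretation of the HC results. A small adjusted midluteal-midfollicular contrast could occur although expression does change across the cycle, so it could not by itself show that there is no cyclical change.

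**Working it through.** The documents give no effect size, power or other figure for the Aim 3 HC contrasts, so there is no figure to reproduce. The check is algebra, followed by an illustration with assumed inputs.

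**Algebra.** Scale mean ALLO to 1 midluteal (ML), p perimenstrual (PM) and 0 midfollicular (MF). Let L be the effect carried by ALLO level over the ML-MF gap. Let K be an effect by another route, such as P4, with the same profile across phases. Let D be a withdrawal effect present only perimenstrually.

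| Contrast | Total | Adjusted for visit-level ALLO |
|---|---|---|
| ML − MF | L + K | K |
| PM − MF | p(L + K) + D | pK + D |
| ML − PM | (1 − p)(L + K) − D | (1 − p)K − D |

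- ML − MF loses L. It is zero only if K = 0, with ALLO acting linearly and measured without error.
- PM − MF loses pL, so it is attenuated only if perimenstrual ALLO is above the midfollicular level (p > 0).
- ML − PM can grow or change sign. With L = 0.6 and K = 0: for p = 0 and D = 0.3, the total is 0.6 − 0.3 = +0.30 and the adjusted value −0.30. For p = 0.5 and D = 0.6, the total is 0.3 − 0.6 = −0.30 and the adjusted value −0.60.

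**Illustration.** From the documents: 40 HC, five visits (days +7, +10, +14, +18, +22) and an ALLO intraclass correlation of .29 (SAP, Outcome Specification). Assumed:
- visits +7 and +10 midluteal, +14 and +18 perimenstrual, +22 midfollicular (no mapping is given)
- ALLO means of 1.5, 0.75 and 0 within-person SD, so p = 0.75/1.5 = 0.5
- L + K = 0.60 and D = 0.30, in units where the person variance (0.4) and residual variance (0.6) of expression sum to 1
- a random-intercept model, two-sided 5% tests and 1,000 simulated trials per setting

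Both totals are then 0.60: ML − MF = 0.60, and PM − MF = 0.5 × 0.60 + 0.30.

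| Share via ALLO level | L | K | Adjusted ML − MF, algebra / simulated | Adjusted PM − MF, algebra / simulated | Rejection, adjusted ML − MF |
|---|---|---|---|---|---|
| 100% | 0.60 | 0 | 0 / −0.01 | 0.30 / 0.29 | 5.7% |
| 75% | 0.45 | 0.15 | 0.15 / 0.16 | 0.375 / 0.38 | 14% |
| 50% | 0.30 | 0.30 | 0.30 / 0.31 | 0.45 / 0.46 | 44% |
| 0% | 0 | 0.60 | 0.60 / 0.61 | 0.60 / 0.60 | 93% |

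Without ALLO in the model, the same data give ML − MF of 0.60 with rejection of 95% to 98%.

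**Measurement error.** If ALLO is the sole route but is measured with reliability r (relative to within-person variation around the phase means), about 0.60 × (1 − r) remains: 0.06, 0.12 and 0.24 for r = 0.9, 0.8 and 0.6. The simulation gives 0.06, 0.12 and 0.22.

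**Person-mean ALLO.** This covariate is constant within a person, so it cannot absorb within-person phase differences. The simulation gives 0.60 to 0.61 for ML − MF and 0.59 to 0.61 for PM − MF, against true values of 0.60.

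**The case against.** The best defence is that the adjustment is deliberate. The Premise for Aim 3 treats receptor plasticity to ALLO change as the trigger of perimenstrual symptoms, and holding ALLO level fixed helps to separate withdrawal from level. This stands as a reason to keep the adjusted model. In the illustration the total ML − PM contrast is 0.30 − 0.30 = 0 although D is 0.30, so an unadjusted contrast can hide withdrawal. But section 10.0 gives the adjusted contrasts no such separate role, and withdrawal beyond level is not the midluteal-versus-midfollicular hypothesis.

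The covariate may also be meant as the person's mean, in which case there is almost no loss. That is a possible reading, but the text does not say so.

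The group-by-phase model in section 10.0 names no ALLO covariate and includes HC, so unadjusted HC contrasts could be derived from it. Its stated test, however, is the interaction.

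Finally, section 2.0 introduces this work as "Exploratory substudy of healthy controls (HC"), and no power is claimed for these contrasts. That limits the weight of the point. The hypotheses are still directional, and the planned test should match them.

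A reader might go further and infer that the protocol's own premise predicts a null adjusted midluteal-midfollicular contrast. The documents do not support that. Section 2.0 names P4 as well as ALLO, section 10.0 defines the phases by both hormones, and nowhere is ALLO level called the only route. With another route or assay error, the contrast shrinks but does not vanish.

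**Conclusion.** The point holds conditionally. If the covariate is visit-level ALLO, the stated HC contrasts do not estimate the total phase differences in section 3.0. The midluteal-midfollicular contrast is attenuated by the part that concurrent ALLO carries. The perimenstrual-midfollicular contrast is attenuated only if perimenstrual ALLO exceeds the midfollicular level, and the midluteal-perimenstrual contrast can be enlarged or reversed.

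The direction follows from the protocol's own account, taking level and withdrawal effects to act in the hypothesised direction. The size does not: the ALLO means, effect sizes, reliability and visit-to-phase mapping are all assumed, and the share carried by ALLO is unknown. A reader might also infer that the investigators will report a null adjusted contrast as absence of cyclical change; the documents do not say how a null would be read. What is firm is that the ALLO term is undefined and that no unadjusted HC contrast is stated. Aims 1 and 2 are unaffected.

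**What to change.** In Protocol section 10.0, under normative cyclical change in the HC group:

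1. Make the pairwise phase contrasts without visit-level ALLO the main HC test of the section 3.0 hypothesis.
2. Keep the contrasts adjusted for person-centred visit-level ALLO as a labelled secondary analysis of phase or withdrawal effects beyond concurrent ALLO level.
3. State the form of the ALLO term, and report both sets of contrasts.

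The cost is a change of wording and one extra model per gene. No further visits, samples or assays are needed.
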